1.0 Version Date: 25 April 2019

Version Number:

Template No: CS\_TP\_BS016 – Revision 5 Reference: CS\_WI\_BS005 Effective Date: 01Apr2018

Palladio Biosciences STATISTICAL ANALYSIS PLAN: PROTOCOL PA-102 Page 28 of 36

• Shift from baseline to all visits assessed against normal criteria (low, normal, high)

Table 3 Vital Signs Normal Criteria

Variable	Unit	Low	High
SBP	mmHg	< 90 mmHg	> 140 mmHg
DBP	mmHg	< 50 mmHg	> 90 mmHg
Pulse	bpm	< 60 bpm	> 100 bpm
Respiratory rate	breaths/min	< 12 breaths/min	> 20 breaths/min
Body temperature	°C	< 36.1 °C	> 37.2 °C

All vital sign data will be listed individually by each subject based on the Safety Analysis set. Assessment windows are presented in Table 12-2 in Appendix 3 of the protocol.

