- ⁵ Clinical labs: hematology, clinical chemistry (including liver function), and urinalysis at approximately the same time of day (in the morning and, on dosing days, before the lixivaptan dose). The list of analytes is shown in [Table 6-1](#). Lab tests that need to be repeated during Screening may be obtained through the services of an at-home nursing service provided by the Sponsor.
- ⁶ Serum creatinine will be measured as part of the clinical laboratory assessment.
- ⁷ 12-lead ECG at Screening, Day 1 pre-dose, and prior to discharge from clinic on Day 8. Electrocardiograms to be obtained following 5 minutes rest in supine or semi-recumbent position. The same position must be used throughout the study for a given subject.
- ⁸ Vital signs will be measured following 5 minutes rest in a seated position. Systolic and diastolic blood pressure, pulse rate, respiratory rate, body temperature will be measured at the following time points: prior to Day -1 procedures, prior to discharge from CRU on Day 8, and at the End of Study visit. In addition, blood pressure and pulse rate will also be measured before each administration of study medication in the CRU.
- ⁹ Complete physical examination at Screening, and prior to discharge on Day 8. Brief physical examination on Day -2 or Day -1. Symptom-directed physical examinations as needed.
- ¹⁰ Adverse events and SAEs that are related to study participation (e.g., protocol-mandated intervention) will be recorded from the time the subject signs the informed consent form until exit from the study. All other AEs and SAEs will be recorded from the first dose of lixivaptan until exit from the study.
- ¹¹ Record daily fluid intake on Day -1, Day 1 and Day 7. On Day -1, measurement will begin 24 hours before the expected time of first study medication on Day 1 AM. On Day 1 and Day 7, measurements will begin immediately before the AM dose and will continue for 24 hours into the morning of Day 2 and Day 8, respectively.
- ¹² Subjects will take study medication in the AM and PM for 7 days. Subjects will be asked to record each dose of the study product taken on an outpatient basis in the Study Dosing Diary. Subjects will be asked to bring the Study Dosing Diary together with their unused study product at each visit to the CRU.
- ¹³ PK blood collection timepoints:
Day 1: 0, 1, 2, 4, 6, 9, 10, 11, 12, 14, and 16 hours post AM dose. The collections at 0 and 10 hours are immediately before the AM and PM doses, respectively;

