#### 16.3. LABORATORY EVALUATIONS

Central laboratory results will be included in the reporting of this study for hematology, clinical chemistry (including liver function) and urinalysis. A list of laboratory assessments to be included in the outputs is included in Table 6-1 of the protocol. Assessment windows for laboratory evaluations are presented in Table 12-2 of the protocol. Presentations will use SI units, as provided by the laboratories.

Protocol-specified clinical laboratory tests will be summarized using descriptive statistics.

Clinical laboratory data collected during study conduct which were not required per protocol, such as for special testing to evaluate an AE, will be listed separately and not summarized.

Quantitative laboratory measurements reported as "< X", i.e. below the lower limit of quantification (BLQ), or "> X", i.e. above the upper limit of quantification (ULQ), will be converted to X for quantitative summaries, but will be presented as recorded, i.e. as "< X" or "> X", in the listings.

The following summaries will be provided for laboratory data by cohort at each scheduled timepoint:

- Actual and change from baseline (descriptive statistics n, mean, SD, median, minimum and maximum for quantitative measurements; frequency and proportion for categorical measurements)
- Shift from baseline (normal, low, high) to last observation on treatment (continuous

Author: [name]

1.0

Version Date: 25 April 2019

Version Number:

Template No: CS\_TP\_BS016 – Revision 5 Reference: CS\_WI\_BS005

Effective Date: 01Apr2018

Palladio Biosciences STATISTICAL ANALYSIS PLAN: PROTOCOL PA-102 Page 26 of 36

variables only)

- Individual data listings of laboratory results, with values outside the laboratory's
  reference range flagged as low or high. Clinical laboratory reference/normal ranges
  will be included in the listing.
- For urinalysis, shift tables comparing baseline value to maximum value (using number of subjects with results of negative, trace or positive) for categorical variables
- A listing of serum and urine pregnancy results.

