#### 16.3.1. LABORATORY REFERENCE RANGES

Quantitative laboratory measurements will be compared with the relevant laboratory reference ranges by the lab vendors and categorized as:

- Low: Below the lower limit of the laboratory reference range.
- Normal: Within the laboratory reference range (upper and lower limit included).
- High: Above the upper limit of the laboratory reference range.

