### 16.4. ECG EVALUATION

Results of the ECG assessments will be included in the reporting of this study. Overall evaluation of safety ECGs will be summarized by cohort using descriptive statistics as described in Section 6.1, as well as with frequency counts and percentage of subjects with results classified by the investigator as normal, abnormal – not clinically significant (NCS) and abnormal – clinically significant (CS).

The following ECG parameters will be reported for this study: PR interval, QRS duration, QT

Document: \\leedc-vnasc01\BIOSdata\Palladio\Lixivaptan\\WYA34000\Biostatistics\Documentation\SAP\PA-

102 SAP V1.0 NonPKPD 25APR2019

Author: [name] Version Number: 1.0

Version Date: 25 April 2019

Template No: CS\_TP\_BS016 – Revision 5 Reference: CS\_WI\_BS005

Effective Date: 01Apr2018

Palladio Biosciences STATISTICAL ANALYSIS PLAN: PROTOCOL PA-102 Page 27 of 36

interval (uncorrected), QTcF interval, and heart rate and ventricular rate (beats per minute (bpm)). Values will be obtained directly from the eCRF and no derivations are required.

Assessment windows are presented in Table 12-2 Appendix 3 of the Protocol.

The following summaries will be provided for ECG data for each cohort over each scheduled timepoint:

- Actual ECG parameter values (descriptive statistics for quantitative measurements)
- Shift from baseline interpretation to the investigator interpretation at each time point
- Incidence of abnormal criteria (frequency counts and percentage of subjects as normal/abnormal NCS/abnormal CS)
- · Listing of subjects' individual ECG results

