### 16.5. VITAL SIGNS

The following vital signs measurements will be reported for this study:

- Sitting systolic blood pressure (SBP) and diastolic blood pressure (DBP) (mmHg)
- Pulse rate (beats/minute)
- Respiratory rate (breaths/min)
- Temperature (°C).

The following summaries will be provided for vital signs data at each scheduled timepoint by cohort for the Safety Analysis set using descriptive statistics:

Actual and change from baseline

Incidence of markedly abnormal values

Document: \\ieedc-vnasc01\BIOSdata\Palladio\Lixivaptan\\WYA34000\Biostatistics\Documentation\SAP\PA-

102 SAP V1.0 NonPKPD 25APR2019
Author: [name]

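### Non-PK/PD SAP 16.5 classes a diastolic pressure of exactly 50 mmHg as both normal and markedly abnormal; separately, a worst-value laboratory shift table would be a cheap addition

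*SAP*

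**What the plan says.** **Vital signs (Non-PK/PD SAP 16.5 and 16.5.1).** For each cohort the SAP plans "Incidence of markedly abnormal values" and "Shift from baseline to all visits assessed against normal criteria (low, normal, high". Table 3 gives the low and high limits for the shift table and Table 4 gives the markedly abnormal limits. For DBP, Table 3 sets low at below 50 mmHg and high at above 90 mmHg; Table 4 sets the marked limits at 50 or below and 120 or above. Protocol Table 12-1, footnote 8, adds that "blood pressure and pulse rate will also be measured before each administration of study medication in the CRU".

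**Laboratory data (Non-PK/PD SAP 16.3 and 16.3.1).** The lead-in reads "The following summaries will be provided for laboratory data by cohort at each scheduled timepoint". For continuous variables the shift bullet reads "Shift from baseline (normal, low, high) to last observation on treatment", and protocol 7.7.3 sets the same rule. The categories are low, normal and high only: "Quantitative laboratory measurements will be compared with the relevant laboratory reference ranges by the lab vendors and categorized as" those three classes. The other laboratory outputs are descriptive statistics of actual values and changes, listings with out-of-range flags, and a categorical urinalysis table: "For urinalysis, shift tables comparing baseline value to maximum value".

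**For comparison.** The ECG shift (16.4) is "Shift from baseline interpretation to the investigator interpretation at each time point". Section 6.4 lets unscheduled values contribute to best or worst values and names shift tables as an example.

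**The concern.** Safety and tolerability is a primary objective, read descriptively from cohorts of 8. One subject is 1/8 = 12.5% of a cohort. If one subject has a single DBP reading of 50 and none lower, the markedly abnormal table shows 12.5% for that cohort while the shift table shows no low value. Low blood pressure is relevant to this drug: protocol 1.6 lists orthostatic hypotension among its commonest adverse events, and protocol 5.9 expects an aquaretic effect.

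The laboratory point concerns what the categorical display can show. Protocol 4.2.1 describes mild rises in serum creatinine and sodium as temporary and recoverable. A rise that lasts through dosing is captured by the last on-treatment value. One that appears on Day 2 and settles by the last sample is not, and laboratory variables have no markedly abnormal table beside the shift. Vital signs, ECG and urinalysis are each tabulated at every visit, at every time point or at the maximum.

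**Working it through.** **Step 1: do the Table 4 ranges lie inside the Table 3 ranges?** Table 3 has no normal column, so normal means neither low nor high. Each limit was checked in whole units (0.1 °C for temperature).

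| Variable | Table 3 low | Table 4 low | Low, not marked | Table 3 high | Table 4 high | High, not marked |
|---|---|---|---|---|---|---|
| SBP | < 90 | ≤ 80 | 81–89 (9) | > 140 | ≥ 200 | 141–199 (59) |
| DBP | < 50 | ≤ 50 | none (0) | > 90 | ≥ 120 | 91–119 (29) |
| Pulse | < 60 | ≤ 40 | 41–59 (19) | > 100 | ≥ 120 | 101–119 (19) |
| Respiration | < 12 | ≤ 10 | 11 (1) | > 20 | ≥ 25 | 21–24 (4) |
| Temperature | < 36.1 | ≤ 35.5 | 35.6–36.0 (5) | > 37.2 | ≥ 37.7 | 37.3–37.6 (4) |

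Values that are normal in Table 3 but marked in Table 4: DBP = 50, and no other. Nine of the ten limits nest; the DBP low limit does not. Every DBP that is low is also markedly low, and the marked set is larger than the low set by one value.

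**Step 2: which laboratory draws can fill the shift table?** Protocol Table 12-1 schedules laboratory tests on Days 1, 2, 7, 8 and 35. Its footnote 5 places dosing-day samples before the dose, so the Day 1 sample precedes treatment. Draws after the first dose and before the last are therefore Days 2 and 7. The Day 8 morning sample falls about 24 h after the Day 7 morning dose and 24 − 10 = 14 h after the last dose. Neither document says whether that counts as on treatment, and protocol Table 12-2 omits Day 8 from its laboratory row. In a subject who completes dosing, the shift uses 1 of 2 draws, or 1 of 3 if Day 8 counts.

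**Step 3: what does the last-value rule record?** Illustrative sequences for one analyte, normal at baseline (H = high, N = normal):

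| Day 2, 7, 8 | Last, Day 8 counted | Last, Day 8 not counted | Worst, Day 8 counted | Worst, Day 8 not counted |
|---|---|---|---|---|
| H, N, N | N | N | H | H |
| H, N, missing | N | N | H | H |
| N, H, N | N | H | H | H |
| N, N, H | H | N | H | N |

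The first two rows show the Day 2 excursion missing from the shift under either reading. The last two show that the undefined Day 8 status changes the result. These are patterns, not expected frequencies.

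**The case against.** **The DBP effect is tiny.** It concerns one value in descriptive outputs, with no between-group tests planned, and every reading is listed by subject. All of that stands and is why the point is minor. It does not remove the contradiction. Every Table 3 limit is strict and every Table 4 limit inclusive, so this does not look like a garbled symbol.

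**A reader might size the problem by counting readings.** The protocol schedule gives 8 in-CRU pre-dose readings, less the one before the first dose, plus Days 8 and 35: 8 − 1 + 2 = 9 per subject after the first dose. The visit list in Non-PK/PD SAP Appendix 1 has no Days 2, 4 or 6. On that list the readings are Day 1 evening, Day 7 morning and evening, Day 8 and Day 35: 5 per subject. Neither figure counts readings equal to 50, and the documents give no DBP distribution. No reading count should be used as the size.

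**A reader might infer that the laboratory rule is an error, or that early excursions are lost.** The documents support neither. Protocol 7.7.3 and SAP 16.3 agree on the last value. A Day 2 excursion stays in the flagged listings and in the by-visit statistics where that visit is output (the Appendix 1 list omits Day 2, so this is not assured). If judged clinically significant, it also enters the adverse-event tables. The PK/PD SAP (15.1) separately summarises eGFR, which is derived from creatinine. Protocol 3.1.1 examines reversibility by comparison with four weeks after the last dose, a purpose that an end-of-treatment value suits. The narrower statement survives: no laboratory shift table described in the text shows a resolved excursion.

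**The comparison with other domains is not uniform.** The physical-examination shift (16.6) also uses one endpoint, end of study, although incidences by visit accompany it.

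**A reader might also infer that the retest rule in 6.4 discards abnormal originals.** The text says only that the retest value is used for summaries and that listings keep everything. It is silent on whether a superseded original counts in worst-case or outlier tables. That is at most an optional clarification.

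**Conclusion.** **DBP: wrong as written, minor.** Two planned tables classify a reading of exactly 50 mmHg in opposite ways, and DBP alone among the five vital signs lacks a low-but-not-marked range. One value is affected, at unknown frequency. This is an inconsistency in reporting thresholds; it does not show that low pressure is under-reported. The documents do not say which limit is intended.

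**Laboratory shift: a cheap improvement, not an error.** An out-of-range Day 2 value that normalises by the last on-treatment sample is in no laboratory shift table, though it can be seen elsewhere as described above. How often this will happen cannot be estimated from the documents. The undefined status of the Day 8 sample is a real gap, because it can change which category is recorded.

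Both conclusions rest on the SAP text. The table templates it refers to are not among the documents and could already settle some details.

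**What to change.** - **SAP 16.5 and 16.5.1:** reconcile the two DBP low limits so that the markedly low range lies inside the low range. The sponsor must say which limit was meant. Treating 50 alike in both tables reduces the conflicting values from 1 to 0; if both limits stay at 50, the intermediate range remains empty.
- **SAP 16.3:** keep the last-value table and state whether the Day 8 sample counts as on treatment. Add a shift from baseline to the worst on-treatment value, with lowest and highest taken separately and unscheduled values included. Exclude Day 35 or show it separately, since it is four weeks off drug.
- **SAP 6.4 (optional):** one sentence on whether an original value superseded by a retest still counts in worst-case and outlier tables.

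The cost is a few words and one extra table from data already collected. The worst-value table will pick up some chance excursions, so it belongs beside the last-value table, not in its place. It will also show no movement for a subject already high at baseline.

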#### 16.5.1. VITAL SIGNS MARKEDLY ABNORMAL CRITERIA

Markedly abnormal quantitative vital signs measurements will be identified in accordance with the following predefined criteria:

Document: \(\liedc-vnasc01\BIOSdata\Palladio\Lixivaptan\WYA34000\Biostatistics\Documentation\SAP\PA-102 SAP V1.0 NonPKPD 25APR2019

Author: [name] Version Number:

Version Date: 1.0

Version Date: 25 April 2019

Template No: CS\_TP\_BS016 - Revision 5 Reference: CS\_WI\_BS005

Effective Date: 01Apr2018

Palladio Biosciences STATISTICAL ANALYSIS PLAN: PROTOCOL PA-102 Page 29 of 36

Table 4 Vital Signs Markedly Abnormal Criteria

Variable	Unit	Low	High
SBP	mmHg	≤ 80 mmHg	≥ 200 mmHg
DBP	mmHg	≤ 50 mmHg	≥ 120 mmHg
Pulse	bpm	≤ 40 bpm	≥ 120 bpm
Respiratory rate	breaths/min	≤ 10 breaths/min	≥ 25 breaths/min
Body temperature	°C	≤ 35.5 °C	≥ 37.7 °C

### 16.6. PHYSICAL EXAMINATION

All physical examination findings, including non-scheduled symptom-directed examination results, will be listed individually for each scheduled timepoint, including specification of any abnormalities observed. Incidences of physical examination results (Normal, Abnormal NCS, Abnormal CS) for every visit, as well as a shift table summarizing the changes in physical examination assessments (Normal, Abnormal NCS, Abnormal CS) from baseline to EOS will be provided, using counts and percentages for each cohort. New abnormalities occurring after administration of study medication will be recorded as adverse events.

#### 16.7. OTHER SAFETY ASSESSMENTS

Tolerability data obtained from the Questionnaire for Tolerability will be listed for all subjects. Frequencies and proportions of responses to questions will be summarized by cohort and

Document: \\leedc-vnasc01\BIOSdata\Palladio\Lixivaptan\\WYA34000\Biostatistics\Documentation\SAP\PA-

102 SAP V1.0 NonPKPD 25APR2019
Author: [name]

Version Number: 1.0

Version Date: 25 April 2019

Template No: CS\_TP\_BS016 – Revision 5 Reference: CS\_WI\_BS005

Effective Date: 01Apr2018

Palladio Biosciences STATISTICAL ANALYSIS PLAN: PROTOCOL PA-102 Page 30 of 36

dose.

### 17. DATA NOT SUMMARIZED OR PRESENTED

Details of admission and discharge from the CRU and follicle-stimulating hormones test results will not be summarized or presented, but will be available in the clinical study database, SDTM and/or ADaM datasets.

 ${\tt Document:} \qquad {\tt \underline{\label{losdata}Palladio}\label{losdata} Palladio} \\ {\tt \underline{\label{losdata}}\label{losdata} Palladio} \\ {\tt \underline{\label{losdata}}\label{losdata} Palladio} \\ {\tt \underline{\label{losdata}}\label{losdata} Palladio} \\ {\tt \underline{\label{losdata}}\label{losdata}\label{losdata} Palladio} \\ {\tt \underline{\label{losdata}}\label{losdata}\label{losdata}\label{losdata} Palladio} \\ {\tt \underline{\label{losdata}}\label{losdata}\label{losdata}\label{losdata}\label{losdata}\label{losdata}\label{losdata} Palladio \\ {\tt \underline{\label{losdata}}\label{losdata}\label{losdata}\label{losdata}\label{losdata}\label{losdata}\label{losdata}\label{losdata}\label{losdata}\label{losdata}\label{losdata}\label{losdata}\label{losdata} Palladio \\ {\tt \underline{\label{losdata}}\label{losdata}\l$ 

102 SAP V1.0 NonPKPD 25APR2019

Author: [name] Version Number: 1.0

Version Date: 25 April 2019

Template No: CS\_TP\_BS016 - Revision 5 Reference: CS\_WI\_BS005

Effective Date: 01Apr2018

Palladio Biosciences STATISTICAL ANALYSIS PLAN: PROTOCOL PA-102 Page 31 of 36

## **APPENDIX 1. Programming Conventions for Outputs**

#### **OUTPUT CONVENTIONS**

Outputs will be presented according to the IQVIA Global Biostatistics Standard Output Conventions, which is available upon request.

#### **DATES & TIMES**

Depending on data available, dates and times will take the format dd-mmm-yyyy; times will take the format hh:mm:ss; combined dates and times will take the format dd-mmmyyyyThh:mm:ss.

#### **SPELLING FORMAT**

English US.

### **PRESENTATION OF TREATMENT GROUPS**

For outputs, treatment groups will be represented as follows and in that order:

Treatment group	Treatment label
CKD1/2 200 mg	Cohort 1
CKD3 200 mg	Cohort 2

\\ieedc-vnasc01\BIOSdata\Palladio\Lixivaptan\WYA34000\Biostatistics\Documentation\SAP\PA-Document: 102 SAP V1.0 NonPKPD 25APR2019

Author: [name] Version Number:

1.0 25 April 2019

Version Date:

Template No: CS\_TP\_BS016 - Revision 5 Reference: CS\_WI\_BS005

Effective Date: 01Apr2018

Palladio Biosciences STATISTICAL ANALYSIS PLAN: PROTOCOL PA-102 Page 33 of 36

CKD1/2 50 mg	Cohort 3
CKD3 50 mg	Cohort 4
Not allocated to a cohort	Not allocated

### **PRESENTATION OF VISITS**

For outputs, visits will be represented as follows and in that order:

Long Name (default)	Short Name
Screening	Screening
Day -1	D-1
Day 1	D1
Day 7	D7
Day 8	D8
Day 9	D9
Day 10	D10
Day 11	D11
End of Study (Day 35)	EOS

Document: \(\liedc-vnasc01\BIOSdata\Palladio\Lixivaptan\WYA34000\Biostatistics\Documentation\SAP\PA-

102 SAP V1.0 NonPKPD 25APR2019

Author: [name] Version Number: 1.0

Version Date: 25 April 2019

Template No: CS\_TP\_BS016 - Revision 5 Reference: CS\_WI\_BS005

Effective Date: 01Apr2018

Palladio Biosciences STATISTICAL ANALYSIS PLAN: PROTOCOL PA-102 Page 34 of 36

### **PRESENTATION OF NOMINAL TIMES**

For outputs, nominal times will be represented as follows:

Long Name (default)	Short Name
Day 1 (0 hr)	D1_0h
Day 1 (1 hr)	D1_1h
Day 1 (2 hr)	D1_2h
Day 8 (0 hr)	D8_0h
Day 8 (10 hr)	D8_10h

#### LISTINGS

All listings will be ordered by the following (unless otherwise indicated in the template):

- Cohort
- Center-Subject ID (note no dash in actual output, e.g. Center 01, Subject 01 is 0101, by earliest enrolled to latest enrolled within the cohort),
- Date (where applicable),
- For listings where subjects not allocated to a cohort are included, these will appear in a category after the cohorts labelled 'Not allocated'.

Author: [name]

Version Number: 1.0

Version Date: 25 April 2019

Template No: CS\_TP\_BS016 - Revision 5 Reference: CS\_WI\_BS005

Effective Date: 01Apr2018

Palladio Biosciences STATISTICAL ANALYSIS PLAN: PROTOCOL PA-102 Page 35 of 36

## **APPENDIX 2. Partial Date Conventions**

The only items that may have partial dates are medical history start/end dates, CKD initial diagnosis date and AE start/end dates. All other dates collected in the study should be a complete date with dd-mmm-yyyy format.

### **ALGORITHM FOR TREATMENT EMERGENCE OF ADVERSE EVENTS:**

START DATE	STOP	ACTION
	DATE	
Known	Known	If start date < study med start date, then not
		TEAE
		If start date >= study med start date, then TEAE
	Partial	If start date < study med start date, then not
		TEAE
		If start date >= study med start date, then TEAE
	Missing	If start date < study med start date, then not
		TEAE
		If start date >= study med start date, then TEAE
Partial, but known	Known	Not TEAE
components show that		

 ${\tt Document:} \qquad {\tt \underline{\label{losdata}Palladio}\label{losdata} Palladio} \\ {\tt \underline{\label{losdata}}\label{losdata} Palladio} \\ {\tt \underline{\label{losdata}}\label{losdata} Palladio} \\ {\tt \underline{\label{losdata}}\label{losdata} Palladio} \\ {\tt \underline{\label{losdata}}\label{losdata}\label{losdata} Palladio} \\ {\tt \underline{\label{losdata}}\label{losdata}\label{losdata}\label{losdata} Palladio} \\ {\tt \underline{\label{losdata}}\label{losdata}\label{losdata}\label{losdata}\label{losdata}\label{losdata}\label{losdata} Palladio \\ {\tt \underline{\label{losdata}}\label{losdata}\label{losdata}\label{losdata}\label{losdata}\label{losdata}\label{losdata}\label{losdata}\label{losdata}\label{losdata}\label{losdata}\label{losdata}\label{losdata} Palladio \\ {\tt \underline{\label{losdata}}\label{losdata}\l$ 

102 SAP V1.0 NonPKPD 25APR2019

Author: [name] Version Number: 1.0

Version Date: 25 April 2019

Template No: CS\_TP\_BS016 - Revision 5 Reference: CS\_WI\_BS005

Effective Date: 01Apr2018

Palladio Biosciences STATISTICAL ANALYSIS PLAN: PROTOCOL PA-102 Page 36 of 36

START DATE	STOP	ACTION
	DATE	
it cannot be on or after		
study med start date		
	Partial	Not TEAE
	Missing	Not TEAE
Partial, could be on or	Known	If stop date < study med start date, then not
after study med start		TEAE
date		If stop date >= study med start date, then TEAE
	Partial	Assumed TEAE
	Missing	Assumed TEAE
Missing	Known	If stop date < study med start date, then not
		TEAE
		If stop date >= study med start date, then TEAE
	Partial	Assumed TEAE
	Missing	Assumed TEAE

 ${\tt Document:} \qquad {\tt \underline{\label{losdata}Palladio}\label{losdata} Palladio} \\ {\tt \underline{\label{losdata}}\label{losdata} Palladio} \\ {\tt \underline{\label{losdata}}\label{losdata} Palladio} \\ {\tt \underline{\label{losdata}}\label{losdata} Palladio} \\ {\tt \underline{\label{losdata}}\label{losdata}\label{losdata} Palladio} \\ {\tt \underline{\label{losdata}}\label{losdata}\label{losdata}\label{losdata} Palladio} \\ {\tt \underline{\label{losdata}}\label{losdata}\label{losdata}\label{losdata}\label{losdata}\label{losdata}\label{losdata} Palladio \\ {\tt \underline{\label{losdata}}\label{losdata}\label{losdata}\label{losdata}\label{losdata}\label{losdata}\label{losdata}\label{losdata}\label{losdata}\label{losdata}\label{losdata}\label{losdata}\label{losdata} Palladio \\ {\tt \underline{\label{losdata}}\label{losdata}\l$ 

102 SAP V1.0 NonPKPD 25APR2019

Author: [name] Version Number: 1.0

Version Date: 25 April 2019

Template No: CS\_TP\_BS016 - Revision 5 Reference: CS\_WI\_BS005

Effective Date: 01Apr2018

Palladio BiosciencesInsert Customer Name/ Logo PK/PD STATISTICAL ANALYSIS PLAN: PROTOCOL PA-102 Page 1 of 39

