6.1.9 Adverse Events

6.1.9.1 Definitions of Adverse Events

The Investigator is responsible for reporting all AEs that are observed or reported during the study, regardless of their relationship to study drug or their clinical significance, as outlined in [Section 6.1.9.2](#) below.

An AE is defined as any untoward medical occurrence in a subject enrolled into this study regardless of its causal relationship to study drug.

A treatment-emergent AE (TEAE) is defined as any event not present before exposure to study drug or any event already present that worsens in either intensity or frequency after exposure to study drug.

An SAE is defined as any event that results in death, is immediately life threatening, requires in-subject hospitalization or prolongation of existing hospitalization, results in persistent or significant disability/incapacity, or is a congenital anomaly/birth defect. Important medical events that may not result in death, be life threatening, or require hospitalization may be considered SAEs when, based upon appropriate medical judgment, they may jeopardize the subject or may require medical or surgical intervention to prevent one of the outcomes listed in this definition.

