6.1.9.4 Assessment of Severity

AEs should be graded as mild, moderate, severe, life-threatening, or death using the following definitions:

- Mild (Grade 1): Awareness of signs or symptoms, but easily tolerated and of a minor irritant type, causing no loss of time from normal activities. Symptoms do not require therapy or a medical evaluation; signs and symptoms are transient.
- Moderate (Grade 2): Events introduce a low level of inconvenience or concern to the participant and may interfere with daily activities, but are usually improved by simple therapeutic measures; moderate experiences may cause some interference with functioning.

- Severe (Grade 3): Events interrupt the participant’s normal daily activities and generally require systemic drug therapy or other treatment; they are usually incapacitating.
- Life-threatening (Grade 4): Events that place the participant at immediate risk of death or are disabling.
- Death (Grade 5): Events that result in death.

Changes in the severity of an AE should be documented to allow an assessment of the duration of the event at each level of intensity to be performed. Adverse events characterized as intermittent do not require documentation of onset and duration of each episode.

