### 16.1. ADVERSE EVENTS

Adverse events (AEs) will be coded using the most recent version of MedDRA.

Treatment emergent adverse events (TEAEs) are defined as any event not present before exposure to study drug and subsequently started, or any event already present that worsens in either intensity or frequency, after exposure to study drug. An algorithm for determining whether AE is treatment-emergent if AE start date or AE end date is unknown is described in Appendix 2.

Any AEs and serious adverse events (SAEs) related to study participation (e.g., protocol-mandated intervention) will be recorded from the time the subject signs the informed consent form until the start of study treatment. All other AEs and SAEs will be recorded from

Document: \liedc-vnasc01\BIOSdata\Palladio\Lixivaptan\WYA34000\Biostatistics\Documentation\SAP\PA102 SAP V1.0 NonPKPD 25APR2019

Author: [name] Version Number:

Version Date: 1.0

Version Date: 25 April 2019

Template No: CS\_TP\_BS016 – Revision 5 Reference: CS\_WI\_BS005

Effective Date: 01Apr2018

Palladio Biosciences STATISTICAL ANALYSIS PLAN: PROTOCOL PA-102 Page 23 of 36

the start of study treatment until exit from the study.

Any abnormal laboratory test results (hematology, clinical chemistry, or urinalysis) or other safety assessments (e.g., ECGs, vital sign measurements), including those that worsen from baseline, deemed to be clinically significant in the medical and scientific judgment of the investigator are to be recorded as AEs or SAEs. Any safety assessments that are associated with the underlying disease, unless judged by the investigator to be more severe than expected for the subject's condition, are not to be reported as AEs or SAEs.

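### The Appendix 2 algorithm of the Non-PK/PD SAP classes adverse events with a pre-dose start as not treatment-emergent without testing for worsening, which conflicts with the definition in section 16.1

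*SAP*

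**What the plan says.** **Definition.** Non-PK/PD SAP section 16.1 has two limbs: an event absent before exposure that then starts, "or any event already present that worsens in either intensity or frequency, after exposure to study drug". Protocol section 6.1.9.1 carries the same second limb: "any event already present that worsens in either intensity or frequency after exposure to study drug".

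**Algorithm.** Appendix 2 decides by dates. For a known start date the table gives "If start date < study med start date, then not" TEAE, and "If start date >= study med start date, then TEAE". The pair is repeated for known, partial and missing stop dates. A partial start date that cannot be on or after first dose is also not a TEAE, whatever the stop date.

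**Scope.** Section 16.1 calls on the algorithm "if AE start date or AE end date is unknown", but the table also has rows for fully known dates.

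**Recording.** Under protocol section 6.1.9.2, only events tied to taking part in the study are recorded as adverse events before treatment starts. Other new symptoms during screening go to medical history. Under section 6.1.9.3, a condition present at screening becomes an adverse event if it deteriorates. Section 6.1.9.4 adds: "Changes in the severity of an AE should be documented to allow an assessment of the duration of the event at each level of intensity", and "Adverse events characterized as intermittent do not require documentation of onset and duration of each episode".

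**The concern.** A programmer who codes Appendix 2 as written has no branch for worsening, because the second limb of the definition never reaches the table. An event that carries a pre-dose start date and becomes more severe or more frequent on lixivaptan would then be left out of the TEAE tables.

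Safety and tolerability are a primary objective and the SAP's primary estimand. The incidence tables planned in section 16.1.2 (by system organ class and preferred term, by severity and by relationship) are all tables of TEAEs, so an event classed as not treatment-emergent survives only in the listings. Where the missing branch has an effect, that effect can only lower TEAE counts.

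**Working it through.** The plan gives no figure on this point, so the check is to run the table against the definition.

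**Step 1. Classify each start-date state under Appendix 2.**

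| Start date | Stop date known, before first dose | Stop date known, on or after first dose | Stop date partial or missing |
|---|---|---|---|
| Known, before first dose | Not TEAE | Not TEAE | Not TEAE |
| Partial, must be before first dose | Not TEAE | Not TEAE | Not TEAE |
| Partial, could be on or after first dose | Not TEAE | TEAE | TEAE |
| Missing | Not TEAE | TEAE | TEAE |
| Known, on or after first dose date | TEAE | TEAE | TEAE |

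**Step 2. Apply the definition to an event present before dosing that worsens afterwards.** Such an event must be ongoing after first dose, so its stop date is on or after first dose, partial or missing. The definition gives TEAE in every case. The algorithm gives not TEAE in the first two rows. The conflict is confined to those rows, because the other three return TEAE for such an event.

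**Step 3. Ask which records can reach those two rows.**

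- A participation-related event recorded between consent and first dose has a genuine pre-dose start. If it persists and then worsens on drug, and the worsening is documented on the same record, it falls in the first or second row.
- A condition held in medical history that deteriorates after dosing becomes an adverse event under protocol section 6.1.9.3. That section collects a time of onset but does not say whether this means the original onset or the date of worsening. If the site enters the worsening date, the record lands in the last row and is counted. If it enters the original onset, the record is not counted.
- The instruction in section 6.1.9.4 to document severity changes does not say whether to use one record or several. For intermittent events, a rise in frequency need not generate a new onset date.

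**Step 4. Scale.** Each cohort is planned at 8 subjects, 32 in all. For a given preferred term, each subject whose only event of that term is misclassified changes the incidence by:

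- cohort: 1/8 = 12.5 percentage points
- all subjects: 1/32 = 3.1 percentage points

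The number of such subjects, k, is not in the documents. As an assumed range for one cohort, the loss is k/8:

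| k | Points lost in the cohort | Points lost in all 32 |
|---|---|---|
| 0 | 0 | 0 |
| 1 | 12.5 | 3.1 |
| 2 | 25.0 | 6.3 |
| 4 | 50.0 | 12.5 |

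These rows show the granularity of a small cohort. They do not estimate the error.

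**The case against.** The strongest reply is that few records can reach the faulty rows.

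- Before dosing, only participation-related events are adverse event records. Pre-existing nocturia, thirst or headache sits in medical history and has no pre-dose adverse event record to misclassify. If it deteriorates, the adverse event exists only because of the deterioration, so its natural onset is the post-dose worsening, which Appendix 2 counts.
- Severity changes could be kept as separate dated records, in which case the algorithm works. The eCRF that would settle this is not among the documents.
- Section 16.1 states the governing definition and calls on the algorithm only for unknown dates, under an appendix about partial dates.
- Ambiguous and missing dates default to TEAE unless a known stop date precedes first dose. An event dated on the first-dose day is a TEAE even if it began before the dose. The rules therefore also over-count in places.
- All adverse events are listed, safety is analyzed descriptively, and aquaretic burden has its own questionnaire.

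Most of this stands as a limit on size. It does not remove the mismatch. The fully known rows make the table work as the general rule, and no other operational rule is given. The new-record and worsening-date conventions on which the defence relies are not written down. The questionnaire is completed only on Days 2 and 7, with no pre-dose administration, so it cannot itself show worsening from the pre-treatment state.

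**Conclusion.** The conflict between definition and algorithm is real and lies in the text of the SAP. It affects adverse events with a known start, or a partial start that must fall, before first dose and that worsen after exposure. The clear exposure is a participation-related event that persists and worsens. The conditional exposure is a deteriorated pre-existing condition entered with its original onset. The number of subjects is unknown, probably small and possibly zero. Each one moves a term's cohort incidence by 12.5 points, and the event remains in the listings.

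A reader might infer three stronger conclusions that the documents do not support:

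- *Every event present before dosing is lost.* Events with ambiguous or missing start dates that continue past first dose are counted.
- *The drug's expected effects, such as nocturia, thirst or headache, will drop out of the tables.* That requires a site to back-date the record to the original onset, which the text neither requires nor rules out. The exclusion criteria do indicate that nocturia is expected in these patients. The documents do not say the same of thirst or headache.
- *The data needed are already collected.* The items listed in protocol section 6.1.9.3 include onset, resolution and severity, but no date of severity change and nothing on change in frequency.

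This should be corrected, as a clarification with a limited expected effect on the results.

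**What to change.** 1. State in the SAP and in the eCRF completion instructions that a post-dose worsening, in intensity or frequency, of a pre-existing event or condition is entered as a new adverse event record whose start date is the date of worsening. This is the main fix, because it covers frequency as well as severity and lets the existing last row of the algorithm work.
2. As a backstop, amend the pre-dose-start rows of Appendix 2 (known, and partial but necessarily before first dose) to read: not TEAE unless recorded as worsened on or after first dose.
3. Reword the sentence in section 16.1 that introduces the algorithm so that its scope matches the table.

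The cost is a few lines of SAP text and one data-entry instruction. Records already entered with a pre-dose start should be checked before database lock. Any that worsened on drug need the date of worsening confirmed with the site. For changes in frequency this may be information not yet collected.
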